7.6 Overall Survival

The OS is defined as time from the first day of treatment to the date of death. A subject alive at the end of study or lost to follow-up will be censored for OS at the last date when the subject was known to be alive, i.e., the last date on study.

If data warrants, the median and quartiles of OS and their 95% CIs will be assessed using the Kaplan-Meier method. Brookmeyer-Crowley method will also be used for the confidence interval calculation. The proportion of subjects alive at 3 months, 6 months and other timepoints of interest will be estimated using the Kaplan-Meier method. OS will be summarized and listed for the All-Treated population.

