3.9 Lost to Follow-Up

- A subject will be considered lost to follow-up if he or she repeatedly fails to return for scheduled visits and is unable to be contacted by the study site.
- The following actions must be taken if a subject fails to return to the clinic for a required study visit:
 - The site must attempt to contact the subject and reschedule the missed visit as soon as possible and counsel the subject on the importance of maintaining the assigned visit schedule and ascertain whether the subject wishes to and/or should continue in the study.
 - Before a subject is deemed lost to follow-up, the investigator or designee must make every effort to regain contact with the subject (where possible, 3 telephone calls and, if necessary, a certified letter sent to the subject's last known mailing address or local equivalent methods). These contact attempts should be documented in the subject's medical record.
 - Should the subject continue to be unreachable, she will be considered as lost to follow-up and withdrawn from the study.

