- o. **PLD Administration:** PLD will be administered according to the dosing schedule provided. If the start of a subsequent cycle (e.g., Day 1) is delayed, the current cycle length is extended (e.g., the cycle lasts longer than 28 days). In addition, length of subsequent cycles will remain unchanged (i.e., 28 days for PLD Cohort).
- p. **AE Monitoring:** Subjects will be followed continuously for AEs during the study and for 30 days after the last dose of SL-172154. After a subject is discontinued from SL-172154 due to progressive disease or for other reasons, any ongoing AE should be followed until resolution (or return to baseline) and documented in the eCRF. If another anti-cancer agent is started within 30 days after the last dose of SL-172154, only SAEs and AEs that occur prior to the start of the new anticancer therapy should be recorded. In the event of a continuing SAE, the subject should be asked to return for follow-up until the SAE has resolved or is deemed to be continuing indefinitely. AEs will be characterized per NCI-CTCAE criteria v5.0 and events recorded in the eCRF
- q. **Post-Treatment Visit (PTV):** visit should occur 30 days (± 7 days) after the last dose of study treatment. If the subject is going to start a new anticancer therapy before the PTV due date, PTV should be conducted prior to starting the new therapy.
- r. **Survival Follow-Up (SFU):** All subjects will be contacted after discontinuing study treatment to collect survival status. Subjects should be contacted every 3 months (± 14 days) from the PTV until death, withdrawal of consent, lost to follow-up or end of study. Contact may include clinic visit, telephone contact, email or mail, chart review, or obituary notice to document survival status. Initiation of any subsequent anti-cancer therapy should also be reported.

6.1.1 PK, ADA, Cytokines and Receptor Occupancy (SL-172154 + PLD Dose Escalation and Dose Expansion Cohorts)

CYCLE 1	C1D1		C1D8							C1D9	C1D15						
	Predose ¹	2h post EOI	Predose ¹	EOI	0.5h post EOI	1h post EOI	1.5h post EOI	2h post EOI	4h post EOI		Predose ¹	EOI	0.5h post EOI	1h post EOI	1.5h post EOI	2h post EOI	4h post EOI
Blood sample for SL-172154 PK ^{2,3,4,5,6}			X	X	X	X	X	X	X	X	X	X	X	X	X	X	X
Blood sample for SL-172154 ADA ⁶			X								X						
Blood sample for cytokines ^{3,5}			X					X		X		X					X
Blood sample for Receptor Occupancy ^{3,5}			X		X					X		X		X			

CYCLE 2	C2D8								

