5.3.1 Premature Withdrawal and Missing Data

Subjects who prematurely withdraw from the study will be included in analyses up to the time of withdrawal, regardless of the duration of treatment and survival follow-up.

Missing data occurs when any requested data is not provided, leading to blank field on the collection instrument. Answers such as “Not applicable”, “Not evaluable”, etc. are not considered to be missing data and should be displayed as such.

For the time to event endpoints including DOR, PFS and OS, the missing data handling method will be censoring. Censoring mechanisms for these endpoints are described in Section 7.

All time to event endpoints will be analyzed using suitable statistical methods.

In the event that the study is prematurely discontinued, a review will be carried out by the study team to assess which statistical analyses are still considered appropriate.

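### SAP 7.6 treats the date last known alive and the last date on study as one date; they can differ, and OS would be biased upward if the second were programmed

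*SAP*

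**What the plan says.** SAP 7.6 defines the endpoint: "The OS is defined as time from the first day of treatment to the date of death". A subject who is alive at the end of the study, or lost to follow-up, is censored at "the last date when the subject was known to be alive, i.e., the last date on study". SAP 5.3.1 states the general principle, "For the time to event endpoints including DOR, PFS and OS, the missing data handling method will be censoring", and refers to SAP Section 7 for the mechanism. For OS that mechanism is this one sentence. PFS has a full censoring table in SAP 7.5; OS has none.

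The protocol describes how a subject becomes lost. Section 3.9 requires repeated missed visits and then active tracing: "Before a subject is deemed lost to follow-up, the investigator or designee must make every effort to regain contact with the subject". The tracing is, where possible, three calls and, if necessary, a certified letter. Only after that does the status change: "Should the subject continue to be unreachable, she will be considered as lost to follow-up and withdrawn from the study". On survival follow-up, the schedules of assessments in 6.1 and 6.2 say "Subjects should be contacted every 3 months", with a window of 14 days either way, counted from the post-treatment visit.

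**The concern.** The *i.e.* asserts that two dates are the same when the protocol's own process can separate them. A lost subject remains on study until she is declared lost, and that declaration comes after the last moment anyone knew she was alive. A subject who is alive when the sponsor closes the study may have had her last survival contact weeks or months before.

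Censoring at the later date keeps such a subject in the Kaplan-Meier denominator over a period in which her vital status is unknown. Deaths are then divided by too many subjects at risk, and the curve sits too high. The OS table and Kaplan-Meier plot are scheduled for the full report and for the abbreviated one (SAP 13.1 and 13.2). The protocol synopsis quotes OS of 8.4 to 16.8 months for PLD alone, so readers have an obvious benchmark, and an upward shift would flatter the combination.

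**Working it through.** **No planned figure to reproduce.** Neither document attaches a sample size, event count or test to OS. The check is a reading of the text, followed by an illustration of size.

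**1. Can the dates differ?**

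| Subject | Last known alive | Possible last date on study |
|---|---|---|
| Lost to follow-up | Last visit or successful contact | Date declared lost and withdrawn, after missed visits and tracing (protocol 3.9) |
| Alive at closure | Last visit or survival contact | Final data capture or sponsor closure (SAP 3.6) |

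Yes, in both rows. Neither document defines the last date on study. The SAP does use an end-of-study-participation date elsewhere (6.1 for disposition, 6.8 for imputing medication dates), and a programmer could take that variable.

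**2. Inputs for the size**

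- True median OS *m*: 8.4, 12 and 16.8 months. The outer values are the synopsis range for PLD; 12 is an intermediate value.
- Follow-up: 14 months' recruitment in a 25-month study (synopsis), so 25 − 14 = 11 to 25 months per subject.
- Gap *g*: 1, 3 or 3.46 months. The largest is 3 months plus 14 days, and 14/30.4375 = 0.46. Using these as gaps is an assumption.
- Monthly loss rate *λ*: 0.0045, 0.009 or 0.02, giving about 4% to 22% lost. **This is an assumption; the documents give no rate.**
- Exponential survival, and loss unrelated to prognosis. Both are assumptions.

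**3. Formula.** Let μ = ln 2/*m* and *k* = μ + λ. Before 11 months there is no administrative censoring. The ratio of lost-but-still-counted subjects to those truly under observation is

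r(t) = (λ/k) × (exp[k × min(t, g)] − 1).

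The estimated hazard becomes μ/(1 + r(t)) instead of μ, and S(x) = exp(−∫₀ˣ μ/(1 + r(t)) dt).

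Example with *m* = 12, λ = 0.009 (about 9% lost), *g* = 3:

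- μ = 0.0578 and k = 0.0668.
- From month 3, r = (0.009/0.0668) × (exp(0.200) − 1) = 0.030, so the hazard is about 3% too low.
- 3-month OS: 0.841 becomes 0.843 (+0.2 points).
- 6-month OS: 0.707 becomes 0.712 (+0.5 points).

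**4. Simulation (400,000 subjects per scenario).** Each cell gives censoring at last known alive, then censoring lost subjects *g* months later.

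| True median (months) | Lost | Gap (months) | 3-month OS | 6-month OS | Median OS (months) |
|---|---|---|---|---|---|
| 8.4 | 4% | 1 | 0.780, 0.781 | 0.609, 0.611 | 8.38, 8.43 |
| 8.4 | 16% | 3.46 | 0.781, 0.787 | 0.609, 0.625 | 8.39, 8.93 |
| 12 | 9% | 3 | 0.841, 0.843 | 0.707, 0.712 | 11.99, 12.30 |
| 12 | 19% | 3.46 | 0.841, 0.846 | 0.708, 0.721 | 12.05, 12.85 |
| 16.8 | 22% | 3.46 | 0.882, 0.886 | 0.779, 0.789 | 16.72, 17.90 |

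Over all 27 scenarios the formula gives shifts of 0.04 to 0.62 points at 3 months and 0.08 to 1.65 points at 6 months, in line with the simulation. The simulated median moves by about 0.05 to 1.2 months. Censoring at last known alive recovers the true curve.

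**5. Subjects alive at closure.** These are not in the simulation. With follow-up of at least 11 months, a gap of 3.46 months would begin no earlier than 11 − 3.46 = 7.54 months. If the study runs to plan, this leaves the 3- and 6-month estimates alone, but it could add to the effect on the median.

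**The case against.** The strongest reply is that the sentence already contains the right rule. It names the date last known alive as the censoring date, and what follows only restates it. Where the SAP means administrative exit it uses another term, end of study participation, which supports reading the OS sentence as evidence of life. No programming specification shows otherwise. A reader might infer that the plan does censor OS late and does add unobserved survival time. The documents do not support that, because nothing in them defines the last date on study as the later date.

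Three further points limit the size.

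- A reader might multiply a 10% loss rate by 3.5 months and report 0.35 months of added time per subject. The 10% is not in the documents, the product gives every lost subject the longest contact interval, and added time at risk is not the same as bias in an estimate. On treatment, dosing visits on Days 1, 8 and 15 make gaps much shorter.
- A reader might assume that the effect concentrates in subjects who died unnoticed. The schedules allow survival status to be established by chart review or obituary notice, so follow-up does not depend on reaching the subject.
- Sampling error is far larger at the named time points. With 6-month OS of 0.707, the binomial standard error is √(0.707 × 0.293/70) = 5.4 points for 70 subjects and 10.2 points for 20.

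All of this stands as a limit on severity. It does not rescue the equivalence, which is stated in the text and does not hold under protocol 3.9.

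**Conclusion.** The point holds as an ambiguity that permits a biased derivation; it is not a demonstrated error. The direction under the later-date reading is certain: upward. The size is conditional. Within the assumed loss rates and gaps, the shift is small at 3 and 6 months, and it approaches a month or more on the median only with heavy loss and long gaps. Loss related to poor prognosis was not modelled and could make it larger.

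Severity is low. OS is an exploratory objective with no hypothesis test, it is summarised only if the data warrant, and it is not among the listed outcome measures for choosing the recommended Phase 2 dose. The change is still worth making, because it removes an incorrect equivalence from the only sentence that governs OS censoring.

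**What to change.** In SAP 7.6, delete the clause that begins with *i.e.* Define the OS censoring date as the latest date, on or before data cut-off, with documented evidence that the subject was alive: a visit, dose, laboratory sample, scan or survival contact. State that the same rule applies to subjects who withdraw consent. Protocol 3.8 provides for them, but the SAP sentence names only those alive at study end or lost.

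The cost is an edit to one sentence and one derived-date specification. No new data collection is needed, and no sample size or other endpoint is affected.

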7.7 CA-125

The CA-125 at baseline and post-baseline assessments, and maximum changes in CA-125 from baseline among all post baseline assessments will be summarized. Number of subjects with $\geq 50\%$, $\geq 75\%$ and 100% decreases or increase from baseline will be summarized. The percent change from baseline in CA-125 for all post-baseline assessments over time will be plotted by subject. The CA-125 test results along with change from baseline and percent change from baseline will be presented in data listings.

8. SAFETY ANALYSES

Unless specified otherwise, all safety data summaries will be presented by dose levels for all subjects in the All Treated population for each treatment regimen. Select safety summaries will be provided for DLT evaluable populations.

8.1 Study Drug Exposure

8.1.1 Study Drug Treatment Duration

For SL-172154 + PLD regimen, the study drug treatment duration will be calculated as minimum of (date of death + 1 day, data cutoff date + 1 day, and date of last dose + 7 days if last dose is on D1 (or D8) of a cycle or + 14 days if last dose is on D15 of a cycle) - date of first dose of study treatment.

For SL-172154 + MIRV regimen, the study drug treatment duration will be calculated as minimum of (date of death + 1 day, data cutoff date + 1 day, and date of last dose + 7 days) - date of first dose of study treatment.

Study drug treatment duration will be listed and summarized. Study drug treatment duration will be plotted by subject using a horizontal bar graph with information regarding the time of first PR/CR and the first PD, dose level, best response (RECIST 1.1) and treatment discontinuation information for each subject.

8.1.2 SL-172154

The actual body weight (kg) will be used for SL-172154 dose calculation in all subjects whose body weight is ≤ 100 kg. For subjects with body weight > 100 kg, weight of 100 kg will be used for dose calculation. The subject should be dosed according to their C1D1 weight throughout the study (mg/kg) unless there is $\geq 10\%$ change (increase or decrease) in their weight from the weight recorded at the C1D1 visit, in which case the expected dose will be re-calculated.

The actual dose received (mg) in each dosing day will be calculated as the following:

- Total dose in mg to be administered *(actual total volume received /total volume to be administered)

Total number of doses received, cumulative dose received (mg), average dose received (mg), relative dose intensity, overdose, and infusion outcome (number of infusions completed and interrupted, and number of infusions not completed) will be summarized. Average dose received is calculated as the cumulative dose (mg) that a subject received divided by the total number of doses received.

Relative dose intensity is defined as the total mg of SL-172154 actually infused divided by the total mg of SL-172154 assigned, expressed as a percentage.

SL-172154 administration for individual subjects will be provided in a data listing by cohort (escalation and expansion), dose level, and date of first dose. In addition to the data captured on the CRF page, the actual dose received and the infusion rate for each infusion period and if there is any interruption, will also be calculated and listed.

8.1.3 PLD

PLD (40 mg/m²) will be administered IV on Day 1 of each 28-day cycle for the combination regimen (SL-172154 + PLD). The dose of PLD administered will be based on the subject's body surface area (m²). All subjects should be weighed within 3 days prior to dosing for every cycle. If a subject experiences either a weight loss or gain >10% compared to the weight used for the last dose calculation, the dose of PLD will be recalculated.

Total number of doses received and infusion outcome (number of infusions completed and interrupted, and number of infusions not completed) will be summarized. The cumulative dose (mg/m²), calculated as the cumulative dose (mg) divided by baseline body surface area (m²), will also be summarized as a continuous variable. The number of subjects with cumulative dose >450mg/m² will be provided as well. PLD administration for individual subjects will be provided in a data listing by cohort (escalation and expansion), dose level, and date of first dose.

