3.7.2 Toxicity Management Guidelines for PLD

The toxicity management guidelines provided in this section represent general guidance for AEs that are considered by the investigator to be possibly related or related to treatment with PLD. Dose modifications/interruptions or delays and treatment discontinuation of PLD for toxicity management should comply with local institutional guidelines or the current regional prescribing information for management of AEs related to PLD. If the country-specific prescribing information is more conservative, the current local guidelines should be used including the special precautions for patients who reach lifetime maximums of 450 mg/m².

In the event of significant toxicity, PLD dosing may be delayed and/or dose reduced as described below. In the event of multiple toxicities, dose modification should be based on the worst toxicity observed. **Table 5** describes the dose reductions to be used for AEs that are considered by the investigator to be possibly related or related to treatment with PLD.

Table 5 PLD Dose Reduction for Management of Toxicities

Dose Level	Dose Level Reduction (mg/kg)
Starting Dose	40 mg/m ²
First Dose Reduction	30 mg/m ²
Second Dose Reduction	20 mg/m ²

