5.2 Pegylated Liposomal Doxorubicin (PLD)

PLD (40 mg/m²) will be administered IV on Day 1 of each 28-day cycle. The first dose of PLD (Cycle 1 Day 1) should be administered as 1 mg/min IV infusion; after Cycle 1, if tolerated, subsequent doses of PLD can be delivered as a 1-hour infusion. Refer to the PLD local prescribing information for details regarding preparation, handling, administration, storage, instructions, and precautions. An accurate and current accounting of PLD administered to each subject must be maintained on an ongoing basis by a member of the study site staff throughout the course of the study.

The dose amount required to prepare the PLD infusion solution will be based on the subject's body surface area (m²). All subjects should be weighed within 3 days prior to dosing for every cycle to ensure they did not experience either a weight loss or gain > 10% from the weight used for the last dose calculation. For weight change less than 10% the decision to recalculate the PLD dose can be in accordance with institutional practice. If the subject experienced either a weight loss or gain > 10% compared to the weight used for the last dose calculation, the amount of PLD must be recalculated. Dose capping should not be performed.

In order to mitigate IRRs, a premedication regimen may be administered as per local practice, which may include diphenhydramine 25 to 50 mg IV or oral equivalent, and/or acetaminophen/paracetamol 650 mg IV or oral equivalent. Primary prophylactic use of steroids for nausea/vomiting is not permitted.

Discontinue PLD for burning or stinging sensation or other evidence indicating perivenous infiltration or extravasation. Manage confirmed or suspected extravasation as per institutional practice.

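### Cumulative PLD dose is divided by baseline body surface area although doses are recalculated after weight change, so the mg/m² summary and the count above 450 mg/m² can err in either direction

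*SAP*

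**What the plan says.** SAP 8.1.3 bases the PLD dose on BSA and has it recalculated on this trigger: "If a subject experiences either a weight loss or gain >10% compared to the weight used for the last dose calculation". Protocol 5.2 makes this mandatory: "the amount of PLD must be recalculated. Dose capping should not be performed". Below the trigger it leaves the choice to the site: "For weight change less than 10% the decision to recalculate the PLD dose can be in accordance with institutional practice".

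SAP 8.1.3 then defines the cumulative dose in mg/m² as the total mg "divided by baseline body surface area", to be summarised as a continuous variable. It adds: "The number of subjects with cumulative dose >450mg/m² will be provided as well". Under SAP 5.3.2, baseline is the last value on or before the first dose of any study drug. No section of either document uses the BSA at each cycle for the cumulative figure.

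The 450 threshold comes from the protocol. Section 3.7.2 refers to "special precautions for patients who reach lifetime maximums of 450" mg/m², and Section 1.7.1 links cumulative anthracycline doses approaching 450 to 550 mg/m² with an 11% risk of cardiotoxicity.

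**The concern.** The numerator and the denominator follow different rules. Once a dose has been recalculated, the mg given reflect current BSA, but they are still divided by BSA before treatment. A subject who loses weight and continues at 40 mg/m² receives fewer mg per dose, so the SAP formula reports less than 40 mg/m² for each later dose. A subject who gains weight is reported at more than 40.

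Two reported figures are affected: the continuous summary of cumulative mg/m², for every re-dosed subject, and the count above 450 mg/m², for subjects near the threshold. The count matters because it is the SAP's summary of how many subjects passed a level that the protocol associates with cardiac risk. It is also likely to be small, so one misclassified subject could change it materially.

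**Working it through.** **Inputs.** Planned dose 40 mg/m² on Day 1 of each 28-day cycle (SAP 8.1.3). Reduction levels 30 and 20 mg/m² (Protocol Table 5). BSA = √(height × weight / 3600) (SAP 6.3). Single-agent PLD median PFS 2.1 to 3.7 months (Protocol 1.5.1). The documents give no data on weight change, so every weight change below is assumed. I also assume complete infusions, one weight change with recalculation, and stable weight afterwards.

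**Formulas.** Let dᵢ be the mg/m² level at dose i and BSAᵢ the BSA used to calculate it.

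- SAP value = Σ(dᵢ × BSAᵢ) / BSA at baseline
- Dose as given per m² = Σdᵢ

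Height is fixed, so BSAᵢ / BSA at baseline = √(weight ratio).

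**Check.** The plan states no figure to reproduce. With constant weight both formulas give 12 × 40 = 480.

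**Where the threshold falls.** 11 × 40 = 440 and 12 × 40 = 480, so a full-dose subject first passes 450 at dose 12.

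**Twelve full doses (480), weight loss after dose 2.**

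- 10% loss: 80 + 400 × √0.90 = 459.5. Still counted; cumulative error (480 − 459.5) / 480 = 4.3%.
- 15% loss: 80 + 400 × √0.85 = 448.8. Missed; error 6.5%.
- 20% loss: 80 + 400 × √0.80 = 437.8. Missed; error 8.8%.
- Tipping point: √(weight ratio) = (450 − 80) / 400 = 0.925, so the ratio is 0.8556 and the loss about 14.4%.

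The error on each dose after the loss is 1 − √0.90, 1 − √0.85 or 1 − √0.80, that is about 5%, 8% or 11%. The cumulative error is smaller because the first two doses are unaffected.

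**With dose reductions.** Ten doses at 40 and two at 30 give 460. With a 10.1% loss recalculated from cycle 2, the SAP value is 40 + 420 × √0.899 = 438.2. Recalculated from cycle 7, it is 240 + 220 × √0.899 = 448.6. Both are missed, with a loss only just past the mandatory trigger.

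**Weight gain.** Eleven full doses give 440. With a 10.1% gain recalculated from cycle 2, the SAP value is 40 + 400 × √1.101 = 459.7, which is falsely counted. Recalculated from cycle 6 it is 200 + 240 × √1.101 = 451.8, also falsely counted.

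**How many subjects could be affected.** Dose 12 falls 11 × 28 = 308 days after dose 1, or 308 / 30.4375 = 10.1 months. Assume exponential time on treatment with the single-agent median PFS as its median. The share still treated is then 0.5^(10.1/2.1) = 3.5% to 0.5^(10.1/3.7) = 15%, about 0.7 to 3.0 of 20 subjects. That is before any weight change is required.

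**The case against.** The strongest reply is that little depends on this variable. It is a descriptive exposure summary, and the SAP attaches no stopping rule or dose decision to it. A reader might infer that the formula lets patients pass 450 mg/m² unnoticed and so puts them at risk. The documents do not support that. Precautions at 450 mg/m² are left to prescribing information and local guidelines (Protocol 3.7.2). LVEF is measured every 8 weeks and at the post-treatment visit (Protocol 6.5.6), with its own rule for a fall (Protocol 3.7.2.4). SAP 8.8 lists ECHO change from baseline and flags low values. PLD administration and weight are both listed by subject (SAP 8.1.3 and 8.6), so a subject with 12 doses can be checked by hand.

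The size is also limited. At full dose, with recalculation from cycle 3 as in the example, a miss needs a loss of about 14.4% or more and treatment that ends at dose 12. A 13th dose with the same 15% loss gives 80 + 440 × √0.85 = 485.7, which is counted. Subjects who are never re-dosed are unaffected, provided that the site used the same BSA formula.

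All of this stands, and it confines the point to reporting. It does not make the definition right: a listing that allows a manual correction does not correct the table, and the continuous summary is off for any re-dosed subject, however few doses were given.

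**Conclusion.** The point holds as a reporting error in a minor but safety-related exposure figure. As written, SAP 8.1.3 understates cumulative mg/m² after weight loss and overstates it after weight gain in re-dosed subjects. The count above 450 mg/m² can therefore miss subjects or include them wrongly. In the 12-dose full-dose example the cumulative error is 4.3% to 8.8% for losses of 10% to 20%. After dose reductions, or after weight gain, a change just over 10% can be enough to misclassify a subject.

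It would be wrong to read this as a one-sided undercount, or to suppose that any loss above the 10% trigger hides a subject who passed 450; the examples show otherwise. The sizes rest on assumed weight changes. The expected number of subjects near the threshold rests on an exponential assumption and on PFS for PLD alone, and time on the combination may differ.

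**What to change.** Replace the definition in SAP 8.1.3 with: cumulative PLD dose (mg/m²) is the sum over cycles of the actual mg given divided by the BSA used to calculate that cycle's dose. Base both the continuous summary and the count above 450 mg/m² on that sum.

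Add a fallback, because the documents do not show that the dosing BSA is captured for PLD. Protocol 5.3.2.3 requires sites to document the weight used for each MIRV dose, but Protocol 5.2 has no matching requirement for PLD. Where the dosing BSA is missing, derive it from the weight collected at each cycle and the screening height. Carry forward the last dosing weight unless the change exceeds 10% or the recorded mg, read with the planned dose level, shows that the site recalculated. State this in the SAP as an assumption.

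The cost is a short SAP edit and some programming before database lock. Weight by cycle and screening height are already in the schedule (Protocol 6.1), so the fallback needs no new data, and neither a protocol amendment nor a change to patient management is required.
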